Subjects with known PML infection or evidence of new neurological symptoms or MRI signs within 6 months prior to randomization, which are compatible with a diagnosis of PML infection, will not be eligible for the study. Subjects in whom suspicion of PML or other opportunistic CNS infections has been raised after randomization by new or worsening neurological symptoms combined with results of objective neurological exam or by MRI findings will have the study drug and DMF interrupted, and will be referred to the local MRI department to perform MRI as described in Section [7.2.3](#) which will be reviewed by the MRI safety board [see Section [3.8.3](#)]. The suspicion of PML or other opportunistic CNS infections will be raised if the subjective and objective findings cannot readily be explained by the subject's MS (e.g., a relapse) or another known condition (e.g., abnormal speech due to a dental intervention or limb weakness due to a trauma) not corresponding to exclusion criteria or if signs of PML / other opportunistic CNS infection are present on MRI. The additional diagnostic workup may include lumbar puncture for cerebrospinal fluid (CSF) analysis including test for JCV in CSF. If, based on the results

of the MRI safety board review, other diagnostic tests and clinical symptoms and signs, the suspicion of PML or other opportunistic CNS infections can be ruled out, the investigator will consider re-start of the study drug if the risk/benefit is still considered positive for the subject and if criteria for permanent discontinuation of the study drug have not been met. **NB:** In subjects with suspicion of acute CNS infection, early lumbar puncture and antiviral treatment should be considered.

Progressive multifocal leukoencephalopathy (PML) is an opportunistic infection of the CNS that can lead to death or severe disability. Active replication of the human polyoma JCV in glial cells of the brain, causing lytic death in oligodendrocytes, is the underlying pathobiology of PML. The infection typically arises in severely immunocompromised subjects, e.g., those with HIV infection, malignant disease, or transplanted organs. People with autoimmune rheumatic diseases, especially systemic lupus erythematosus, are also at higher risk of PML [Kappos 2011].

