The subjects in whom the suspicion of PML/other opportunistic CNS infection has been raised by the investigator as described above, will have the study drug and DMF interrupted and will have MRI performed as described in Section 7.2.3, and the site can ask for a review of the MRI by the MRI safety board [see Section 3.8.3]. Further diagnostic workup (such as lumbar puncture for JCV) will be performed at investigator's discretion. Based on the relevant clinical and nonclinical findings, including the MRI evaluation by the MRI safety board if applicable, the investigator will determine the probability of PML/other opportunistic CNS infection. Subjects in whom PML/other opportunistic CNS infection can be ruled out will be eligible for re-start of the study medication. Subjects with definite or probable PML or diagnosis of other opportunistic CNS infection will have the study drug and DMF permanently discontinued and will be managed according to the local practice (e.g., immune reconstitution and high dose corticoids). Subjects with possible PML/other opportunistic CNS infection will be observed off-study drug and assessed with repeated clinical, imaging and/or laboratory exams at the investigator's discretion until the PML/other opportunistic CNS infection

has been ruled out or confirmed. The study drug may be re-started if PML / other opportunistic CNS infection has been ruled out at a later time point.

Case 3: Subject randomized in the study, reporting new or worsening neurological symptoms outside the scheduled visits.

In case a subject contacts the investigator because of new or worsening neurological symptoms, the investigator should see the subject at an unscheduled visit as soon as possible and perform a full neurological exam in order to decide if the symptoms can be explained by a relapse or can be otherwise explained, or if suspicion of PML/other opportunistic CNS infection should be raised. If the findings indicate a relapse, the subject will be referred to the efficacy assessor for EDSS assessment. If the findings raise suspicion of PML/ other opportunistic CNS infection, the subject will have the study drug and DMF interrupted and will have MRI performed as described in Section 7.2.3, and the site can ask for a review of the MRI by the MRI safety board. Further diagnostic workup (such as lumbar puncture for JCV) will be performed at investigator's discretion. The further process will be the same as for Case 2 above.

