Case 4: MRI from a scheduled visit shows findings not typical for MS.

In case the MRI at a scheduled visit shows signs atypical for MS, detected by the neuroradiologist or during the central review by the MIAC, the site and the sponsor will be alerted and the site can ask for a review of the MRI by the MRI safety board. The subject will be invited for an unscheduled visit at which the investigator will interview the subject for neurological signs and symptoms and perform a full neurological exam. In the event of suspicion of PML, the study drug will be interrupted. Based on the full evaluation of the subject, relevant clinical findings and results of any additional investigations, such as lumbar puncture for JCV, the investigator will determine the probability of PML/other opportunistic CNS infection. Subjects in whom PML/other opportunistic CNS infection can be ruled out will be eligible for re-start of the study medication. Subjects with definite or probable PML or diagnosis of other opportunistic CNS infection will have the study drug and DMF permanently discontinued and will be managed according to the local practice (e.g., immune reconstitution and high dose corticoids). Subjects with possible PML/other opportunistic CNS infection will be observed off-study drug and assessed with repeated clinical, imaging and/or laboratory exams at the investigator's discretion until the PML/other opportunistic CNS infection has been ruled out or confirmed. The study drug may be re-started if PML / other opportunistic CNS infection has been ruled out at a later time point.

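### Section 5.1.12.3.1 gives inconsistent instructions for suspected PML or other opportunistic CNS infection after randomization: whether DMF is interrupted, whether MRI safety board review is required, and which infections are covered

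*Protocol*

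**What the plan says.** All the relevant text is in the current protocol, mainly in Section 5.1.12.3.1.

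- **General paragraph.** It applies after randomization, to suspicion of PML or other opportunistic CNS infection. Suspicion may come from symptoms with examination findings or from imaging: the subjects concerned are those with suspicion raised by symptoms and examination "or by MRI findings will have the study drug and DMF interrupted". Imaging alone is enough, because suspicion is also raised "if signs of PML / other opportunistic CNS infection are present on MRI". The subject is referred for an MRI, "which will be reviewed by the MRI safety board", and the board's result is listed first among the grounds on which the suspicion may be ruled out and restart considered.
- **Cases 2 and 3** (scheduled visit; symptoms reported between visits). Study drug and DMF are both interrupted. On review, "the site can ask for a review of the MRI by the MRI safety board". Case 2 uses the board's evaluation only where applicable, and Case 3 then follows Case 2.
- **Case 4** ("MRI from a scheduled visit shows findings not typical for MS"). The site and sponsor are alerted, the site may request board review, and the subject is called to an unscheduled visit. Then: "In the event of suspicion of PML, the study drug will be interrupted". DMF first appears later, where subjects with definite or probable PML, or a diagnosed other opportunistic CNS infection, "will have the study drug and DMF permanently discontinued".
- **Section 3.8.3.** The board reviews, blinded, brain MRIs that local readers select and export when an opportunistic CNS infection is suspected. It reports to the site and passes important findings to the IDMC.
- **Section 5.1.12.8.** DMF is background therapy, named separately from study treatment.

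**The concern.** A site that sees an atypical scheduled scan will turn to Case 4, which is written for that situation. It finds an instruction about study drug and nothing about DMF until PML is definite or probable. The general paragraph, for the same trigger, tells the site to interrupt both. Because Cases 2 and 3 repeat the DMF instruction, its absence from Case 4 can be taken either as a slip or as a deliberate difference.

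The protocol treats this as a serious matter. It describes PML as potentially fatal or severely disabling, and Section 3.4.2 reports PML cases under DMF. What happens to DMF on suspicion is therefore a safety instruction. The MRI safety board is also one of the named risk-mitigation measures (Sections 1.5, 3.4 and 3.4.2) and a channel to the IDMC. If its review is certain in one paragraph and optional in the next, the information reaching the IDMC depends on which paragraph a site follows.

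**Working it through.** No arithmetic applies, because the plan states no figure on this point. The check is a side-by-side reading of Section 5.1.12.3.1.

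| Text | Trigger | Infections named at the interruption step | Drugs named at the interruption step | Board review |
|---|---|---|---|---|
| General paragraph | Symptoms with examination, or MRI findings | PML and other opportunistic CNS infections | Study drug and DMF | Will take place; used for restart |
| Case 2 | Suspicion at a scheduled visit | Both | Study drug and DMF | Site may request; used if applicable |
| Case 3 | Symptoms outside scheduled visits | Both | Study drug and DMF | Site may request; then as Case 2 |
| Case 4 | Scheduled MRI atypical for MS | PML alone | Study drug | Site may request, before suspicion is established |

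1. **Same trigger?** Yes. The general paragraph includes suspicion raised by MRI findings, so a Case 4 subject in whom PML is suspected falls under it too.
2. **Could study drug in Case 4 include DMF?** No. Section 5.1.12.8 separates them, and Case 4 itself names both at permanent discontinuation.
3. **How long does the silence last?** The section calls PML possible when one of three criteria (clinical, MRI, CSF) is positive. A subject with only an MRI finding is in that class. Case 4 keeps such subjects off study drug until the diagnosis is ruled out or confirmed and still does not mention DMF, so the gap covers the whole observation period.
4. **Review.** The general paragraph's statement that review will occur conflicts most directly with Cases 2 and 3, where the MRI is likewise performed after suspicion is raised. In Case 4 the request comes earlier, about the scheduled scan itself, so the conflict there is less direct. Case 4 does not name the board's result among the grounds for the later decision.
5. **Does another section settle it?** Section 3.8.3 says which images the board sees and whom it informs. Section 7.2.3 has the imaging center analyze locally selected images on notification by the site. Neither says whether selection is obligatory once infection is suspected.
6. **Scope.** Case 4's interruption step names PML alone, while its later steps also cover other opportunistic CNS infections. Section 5.1.12.3 separately requires study drug interruption on suspicion of herpes-virus CNS infection, which fills part of this gap but again does not name DMF.

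**The case against.** The strongest defense is that Case 4 omits DMF and does not state a contrary rule. It does not say that DMF continues, and it does not switch off the general paragraph. Read together, a site that left DMF running would depart from the general paragraph. This stands to the extent that a reader who infers that Case 4 instructs sites to continue DMF goes further than the text. It does not remove the problem: the cases are the scenario-specific instructions, no order of precedence is stated, and Cases 2 and 3 show that the authors repeated the DMF instruction where they meant it.

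A second defense is that review is settled by Section 3.8.3, with locally selected images. That narrows the question but leaves the general paragraph's wording in place.

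Three further inferences are tempting and are not supported:

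- **That study drug discontinuation data would differ between readings.** Section 5.1.12.8 ties study drug to permanent discontinuation of DMF. The discrepancy concerns temporary interruption. Study drug is interrupted on suspected PML under every reading, and Cases 2 and 4 agree on permanent discontinuation.
- **That every scheduled scan is exposed.** With the planned mean follow-up of 1.9 years (1.9 × 52 ≈ 99 weeks), about four 24-weekly scans plus one at end of treatment gives 5 × 600 = 3,000 scans. That counts scans performed. Case 4 starts only when a scan looks atypical for MS, and interruption needs the further step of suspected PML.
- **That the review mismatch belongs to Case 4.** It runs through Cases 2 to 4 and is clearest in Cases 2 and 3.

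**Conclusion.** The section is inconsistent as written on three points: DMF at the interruption step (the general paragraph and Cases 2 and 3 against Case 4), board review (the general paragraph against Cases 2 to 4), and the infections covered at Case 4's interruption step. This is a drafting inconsistency in a safety procedure.

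Its size in subjects cannot be calculated, because the protocol gives no expected rate of atypical scans or of suspected PML. It is likely small: Section 3.4.2 reports no PML case with ponesimod and describes the known risk with DMF and fingolimod as substantially lower than with natalizumab, although suspicions would outnumber confirmed cases. The point does not bear on the primary endpoint, alpha, power or sample size. It merits correction because the event is potentially fatal and the ambiguity can persist while the diagnosis is open. The conclusion assumes only that sites will use the case that matches their situation.

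**What to change.** Reconcile the general paragraph of Section 5.1.12.3.1, Cases 2 to 4 and Section 3.8.3 so that together they give:

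1. one instruction on which drugs are interrupted when suspicion is raised, including by a scheduled MRI;
2. one instruction on whether MRI safety board review is mandatory or at the site's request, at which stage, and how its result enters the restart decision;
3. one scope: PML alone, or also other opportunistic CNS infections.

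Which instruction is correct on each point is for the clinical team; this review takes no position. The cost is wording in one section, a matching sentence in Section 3.8.3, and a letter to sites. No analysis, sample size or data collection changes.

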5.1.12.4 Respiratory system

In case of abnormal spirometry results or persistent respiratory symptoms (e.g., dyspnea), the subject will be closely observed, spirometry will be repeated, and study drug discontinuation should be considered, according to the guidance provided in [Table 5](#).

Table 5 Guidance for subject monitoring and discontinuation for PFT decrease and persistent respiratory AEs

Item	Parameter	Guidance
1	If: > 30% decrease from the study baseline FEV ₁ and/or FVC.	Repeat PFT within the next 2 weeks or earlier if clinically indicated. See item 1a, 1b.
1a	If at repeat PFT: > 30% decrease from the study baseline FEV ₁ and/or FVC and, in the opinion of the investigator, this change is clinically significant.	Discontinue study drug and perform FU PFTs.
1b	If at repeat PFT: ≤ 30% decrease from the study baseline FEV ₁ and/or FVC and the subject does not have respiratory symptoms (e.g., cough, dyspnea).	Resume regular PFTs schedule.

AE = adverse event; FEV₁ = forced expiratory volume in 1 second; FU = follow-up; FVC = forced vital capacity; PFT = pulmonary function test.

If clinically significant, persistent respiratory AEs (e.g., dyspnea) are reported, PFTs must be performed and study drug may be interrupted at the discretion of the investigator. In case of study drug interruption, the subject will be closely observed, FU PFTs will be performed, and further diagnostic work-up and consultation with a pulmonologist or other specialist should be considered according to local practice and the clinical situation. Following study drug interruption, if PFTs normalize and lung toxicity is unlikely, study drug may be re-initiated at the discretion of the investigator.

The decision to permanently discontinue study drug will be made after evaluation of all available information concerning concomitant medications, other potential causes of respiratory AEs, and the clinical status of the subject. Further diagnostic work-up and consultation with a pulmonologist or other specialist should be considered according to local practice and the clinical situation.

Subjects experiencing respiratory symptoms and/or reduced pulmonary function during the course of the treatment with the study drug may be prescribed short-acting β_2 agonist (to be used on an 'as needed' basis ['PRN' use]), at the investigator's discretion. If a subject fails to show symptom relief and/or reversibility, additional diagnostic work-up

(e.g., high-resolution computerized tomography, diffusing capacity for the lungs measured using carbon monoxide [DL_{CO}]) and/or permanent study drug discontinuation should be considered at the discretion of the investigator.

In all cases of permanent discontinuation, FU monitoring must be provided until respiratory AEs have resolved and changes in pulmonary function are no longer regarded as clinically relevant, or until medically indicated.

5.1.12.5 Pregnancy

If a subject becomes pregnant while on study drug, study drug **must** be permanently discontinued. The investigator must counsel the subject and discuss the risks of continuing with the pregnancy and the possible effects on the fetus.

5.1.12.6 Liver abnormalities

In case of abnormal liver tests or signs and symptoms suggestive of drug induced liver injury (DILI), the subject will be closely observed, liver tests will be repeated, and study drug discontinuation should be considered according to the guidance provided in [Table 6](#).

Table 6 Guidance for subject monitoring and discontinuation for liver enzyme abnormalities

Item	Laboratory parameter	Guidance
1	ALT or AST $\geq 3 \times$ ULN *	Start close observation. Repeat labs within 72 hours. See items 1a and 1b. * if ALT or AST $\geq 8 \times$ ULN or ALT or AST $\geq 3 \times$ ULN and TBL $\geq 2 \times$ ULN or INR > 1.5 or ALT or AST $\geq 3 \times$ ULN with the appearance of fatigue, nausea, vomiting, right upper quadrant pain or tenderness, fever, rash, and/or eosinophilia ($> 5\%$) and retest cannot be done within 72 hours, permanently discontinue study drug, and perform FU
1a	If at repeated labs, ALT or AST $\geq 3 \times$ ULN $< 8 \times$ ULN	Continue close observation. Repeat labs twice weekly. See items 2a and 2b.
1b	If at repeated labs, ALT or AST $< 3 \times$ ULN	Resume regular labs schedule.
2a	If at repeated labs, ALT or AST $\geq 5 \times$ ULN for > 2 weeks	Permanently discontinue study drug, and perform FU.
2b	If at repeated labs, ALT or AST $\geq 3 \times$ ULN $< 5 \times$ ULN for > 2 weeks	Continue close observation. Repeat labs once or twice weekly.
3	If at repeated labs: ALT or AST $\geq 8 \times$ ULN	Permanently discontinue study drug, and perform FU.

Item	Laboratory parameter	Guidance
	ALT or AST $\geq 3 \times$ ULN and TBL $\geq 2 \times$ ULN or INR > 1.5 ALT or AST $\geq 3 \times$ ULN with the appearance of fatigue, nausea, vomiting, right upper quadrant pain or tenderness, fever, rash, and/or eosinophilia ($> 5\%$)	

ALT = alanine aminotransferase; AST = aspartate aminotransferase; FU = follow-up; INR = International Normalized Ratio; ULN = upper limit of normal range.

Whenever AST or ALT $\geq 3 \times$ ULN are recorded by the central laboratory, an alert will be sent to the principal investigator and the sponsor. The sponsor will contact the principal investigator to ensure that she/he will immediately contact the subject, and ask the subject about any potential symptoms. The subject will be closely observed and will be asked to return to the site as soon as possible after the time of receipt of the alert to repeat the liver enzyme and bilirubin tests by the central laboratory (unless the clinical situation mandates immediate local testing) according to the scheme illustrated in [Table 6](#). Further diagnostic work-up and consultation with a hepatologist or other specialist should be considered, and adequate medical management should be provided according to local practice and the clinical situation. Any clinically relevant finding meeting the definition of an AE will be recorded accordingly in the eCRF.

In case of study drug interruption, the subject will be closely observed and FU liver tests will be performed. Following study drug interruption, if liver tests normalize and drug-related hepatotoxicity is unlikely, study drug may be re-initiated at the discretion of the investigator. Re-initiation following interruption according to the above criteria can only be done once during the study. The decision to permanently discontinue study drug will be made after evaluation of all available information concerning concomitant medications, other potential causes of hepatotoxicity, and the clinical status of the subject. **NB:** The re-initiation is not permitted for situations where study treatment should be permanently discontinued according to [Table 6](#).

In all cases of permanent study drug discontinuation, FU monitoring must be provided until signs and symptoms have resolved and changes in liver function are no longer regarded as clinically relevant or until medically indicated.

5.1.12.7 Ocular abnormalities

In the event of suspected clinically significant findings (e.g., macular edema), an unscheduled OCT examination should be performed. In the case of macular edema confirmed by the local ophthalmologist, the subject must be permanently discontinued from study drug and will be managed and followed up until resolution. Any clinically relevant finding meeting the definition of an AE will be recorded accordingly in the

eCRF. The OSB will receive all information related to suspected cases of macular edema and will perform central review of OCT results and subject data.

Subjects with active uveitis but without macular edema may continue on the study drug but will require additional ophthalmologic assessments as detailed below.

5.1.12.7.1 Guidance for monitoring and management of subjects with uveitis

In case of suspicion of active uveitis (ocular pain, floaters, blurred vision, increased intraocular pressure) at Visit 1 (Screening) or during a scheduled ophthalmological assessment, fluorescence angiography (FA) should be performed (unless contra-indicated according to the ophthalmologist) in addition to the scheduled ophthalmological assessment and OCT, in order to characterize the uveitis. Subjects with suspicion of uveitis occurring during the study treatment but outside scheduled ophthalmological assessment should have a full ophthalmological assessment performed together with FA (unless contraindicated) as soon as possible. If active uveitis can be confirmed and macular edema can be ruled out, the subject may continue in the study without interrupting the study drug. Such subjects will need to be controlled by the ophthalmologist after 1 week, 2 weeks, and 4 weeks after the diagnosis of uveitis has been confirmed and then every 4 weeks throughout the study or until the condition has resolved. These ophthalmological exams should include full ophthalmological assessment (ophthalmological symptoms, assessment of best corrected visual acuity (Early Treatment Diabetic Retinopathy Study [ETDRS] charts), measurement of ocular pressure, preferably with Goldmann applanation tonometry, slitlamp examination of the anterior segment, and dilated indirect funduscopy) as well as OCT. FA may be repeated at the ophthalmologist's discretion. The ophthalmologist will decide what treatment should be given to the subject. If the subject needs to be treated by immunosuppressants prohibited by the protocol, the study treatment has to be discontinued. If uveitis is progressing in spite of treatment, the investigator may consider interrupting or permanently discontinuing the study drug.

